3.5.7 Immunogenicity Assessment

Immunogenicity analysis for Part A will be presented by dose level and in total, analysis for Part A-2 will be presented in total, and analysis for Part B will be presented by cohort and in total. A total for all patients across Part A and Part A-2 will be presented, as will a total for all Part B patients who received NM21-1480, and a total for all patients in any part who received NM21-1480 at the 800 mg dose level.

Immunogenicity status will be summarized for patients in the Safety Set by scheduled time point and overall. For the overall post-baseline summary, a patient will be considered positive for ADAs if they are positive at any scheduled or unscheduled post-baseline assessment. The following immunogenicity categories will be presented:

- Patients with positive post-baseline ADA assessment
 - After missing baseline titer assessment
 - After negative baseline (titer value = 1)
 - After positive baseline titer value > 1
 - After positive baseline titer value > 1 AND increased from baseline
- Patients negative for ADAs at post-baseline
 - After missing baseline titer assessment
 - After negative baseline (titer value = 1)
 - After positive baseline titer value > 1

It will be noted in the analysis whether any patients have a reduced ADA titer value at post-baseline compared with baseline.

Among patients who have a positive post-baseline ADA assessment, descriptive statistics will be presented for the first positive post-baseline titer value and the maximum post-baseline titer value, and the duration from the start of treatment until the first positive ADA assessment will be summarized. A spider plot may be used to present the titer value trajectories over time for patients with positive post-baseline ADA assessment.

To examine the potential relationship between immunogenicity and safety, the frequency and type of AEs may be compared between ADA positive and negative patients.

Neutralizing antibody status will be summarized.

Immunogenicity assessments including ADA titer values, ADA status by timepoint and overall post-baseline, and neutralizing antibody status will be listed by patient.

3.6 Safety Assessment

Safety data will be summarized by actual treatment received (and in total for selected analyses) based on the Safety Population.

For the safety analysis, unless specified otherwise, Part A will be presented by dose level and in total, Part A-2 will be presented in total, and Part B will be presented by cohort and in total.

3.6.1 Dose-Limiting Toxicities (DLTs)

For Parts A, A-2, and B, DLTs are defined in section 7.2.5.1 of the protocol. DLT's will be identified by the investigator and recorded in the eCRF. The number of patients with DLTs will be summarized, and all DLTs will be listed by patient.

3.6.2 Adverse Events (AEs)

AEs will be captured from signing informed consent/HIPAA authorization, through 70 days after the last dose of study drug, as specified in section 9.2.4 of the protocol. Beyond 70 days from the last dose of study drug, only study treatment-related SAEs or late-occurring irAEs should be reported. All AEs will be coded to system organ class and preferred term using MedDRA version 25.0 or later.

Treatment-emergent adverse events (TEAEs) are defined as AEs that occur or worsen on or after the first dose of study drug.

Adverse events of special interest (AESIs) are defined in section 9.2.1.6 of the protocol as:

- Elevations of ALT/AST that are >3-fold above baseline,
- AEs falling under the system order class (SOC) of hepatobiliary disorders (i.e., to cover any potential liver toxicity) Grade 3 or higher,
- SOC of immune system disorders (i.e., to cover cytokine release syndrome and irAEs) Grade 3 or higher,
- Any AE of CTCAE V5.0 Grade 3 or higher,
- Any CTCAE V5.0 Grade 3 or 4 infusion reaction whether or not the event is a DLT or delayed DLT,
- Any AE considered by the Investigator to represent a DLT or delayed DLT.

AESI's will be identified by the investigator and recorded in the eCRF.

Immune-related AEs (irAEs) will be identified by the investigator and recorded in the eCRF.

An overview of AEs will be provided including counts and percentages of subjects (and event counts) with the following types of AEs:

- Any TEAEs (overall, by maximum severity, and grade ≥ 3)
- Any NM21-1480-related TEAEs (overall, by maximum severity, and and grade ≥ 3)
- Any TEAEs of special interest (overall, by maximum severity, and grade ≥ 3)
- Treatment-emergent irAEs
- Any serious AEs (SAEs)
- Any treatment-emergent serious AEs (TESAEs)
- Any NM21-1480-related TESAEs
- Any TEAEs leading to temporary or permanent discontinuation of NM21-1480
- Any AEs leading to death

The number and percentage of patients with AEs will be summarized by system organ class (SOC) and preferred term (PT) for the following types of AEs:

- TEAEs
- Grade ≥ 3 TEAEs

- NM21-1480-related TEAEs
- Grade ≥ 3 NM21-1480-related TEAEs
- TEAEs of special interest
- Treatment-emergent irAEs
- TESAEs
- NM21-1480-related TESAEs

The number and percentage of patients with AEs will be summarized by SOC, PT, and highest CTCAE grade for the following types of AEs:

- TEAEs
- NM21-1480-related TEAEs

All adverse event data will be listed by patient. Additional listings will present SAEs, AESIs, irAEs, TEAEs leading to temporary or permanent discontinuation of NM21-1480, TEAEs leading to discontinuation of study, and AEs leading to death.

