9.2.1.5 Treatment-Emergent Adverse Event

TEAEs are defined as any AE occurring or worsening on or after the first dose of study drug.

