9.2.2 Time Period and Frequency for Collecting AE and SAE Information

Adverse Events occurring after signing informed consent/HIPAA authorization, but before study drug administration are to be recorded as AEs (though unrelated to study drug). All AEs will be collected at the time points specified in the Schedule of Assessments ([Table 7-1](#) and [Table 7-2](#)). All patients who intend to discontinue the study within 70 days after the administration of the last dose of study drug should be followed until resolution and/or stabilization of any study TRAEs and AEs that led to the discontinuation, and should be monitored for 70 days following the last dose of ND021 (NM21-1480) for the occurrence of study TRAEs. These patients should complete Follow-up visits 1 and 2 unless the patient begins a new therapy.

For all Follow-up periods beyond 70 days from the last dose of study drug, only study treatment-related SAEs or late-occurring irAEs should be reported.

At any time after completion of the Follow-up visit, if an Investigator learns of an SAE that can be reasonably related to study drug, they should promptly notify the Sponsor.

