10.6.3 Safety Analyses

All recorded TEAEs will be listed and tabulated by system organ class, preferred term, and dose and coded according to the most current version of Medical Dictionary for Regulatory Affairs (MedDRA). Besides TEAEs, TRAEs (i.e., assessed as at least possibly related to study drug by the Investigator) will be separately listed and tabulated. The incidence of AEs will be tabulated. Vital signs and clinical laboratory test results will be listed and summarized by dose level. Any significant physical examination findings and results of clinical laboratory tests will be listed. ECG listings will be evaluated by the Investigator and abnormalities, if present, will be listed. A separate listing and summary of all irAEs will be provided. Adverse events will be summarized for all reported data and by study part as well as study period, i.e., up to and including 70 days post last dose of study treatment.

Safety data will be presented in tabular and/or graphical format and summarized descriptively by dose cohort and study day, where appropriate. Safety data for Part B may be pooled across dose groups to mirror the efficacy analysis decisions to facilitate an appropriate risk benefit assessment per cohort.

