APPENDIX A: PARTIAL DATE CONVENTIONS

Table 2 Algorithm for Treatment-Emergent Adverse Events

AE Start Date	AE Stop Date	Action
Known	Known	If start date < study drug start date, then not TEAE If start date \geq study drug start date, then TEAE
	Partial	If start date < study drug start date, then not TEAE If start date \geq study drug start date, then TEAE
	Missing or Unknown	If start date < study drug start date, then not TEAE If start date \geq study drug start date, then TEAE
Partial, but the known date components show that it cannot be on or after study drug start date	Known	Not TEAE
	Partial	Not TEAE
	Missing or Unknown	Not TEAE
Partial, could be on or after study drug start date	Known	If stop date < study drug start date, then not TEAE If stop date \geq study drug start date, then TEAE
	Partial	Impute stop date as latest possible date (i.e., last day of month if day is unknown or 31-Dec if day and month are unknown), then: If stop date < study drug start date, then not TEAE If stop date \geq study drug start date, then TEAE
	Missing or Unknown	Assumed TEAE
Missing or Unknown	Known	If stop date < study drug start date, then not TEAE If stop date \geq study drug start date, then TEAE
	Partial	Impute stop date as latest possible date (i.e., last day of month if day is unknown or 31st December if day and month are unknown), then: If stop date < study drug start date, then not TEAE If stop date \geq study drug start date, then TEAE
	Missing or Unknown	Assumed TEAE

TEAE = treatment-emergent AE

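### The SAP plans AE tables on all reported data only and drops, without saying so, the protocol's summary limited to 70 days after last dose, the period before collection becomes selective

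*SAP*

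**What the plan says.** **Collection.** SAP 3.6.2 captures all AEs from consent "through 70 days after the last dose of study drug". After that: "Beyond 70 days from the last dose of study drug, only study treatment-related SAEs or late-occurring irAEs should be reported". Protocol 9.2.2 has the same rule: "For all Follow-up periods beyond 70 days from the last dose of study drug, only study treatment-related SAEs or late-occurring irAEs should be reported". Protocol 9.2.5 and 9.2.6 also keep fatal SAEs reportable after the window, and 9.2.6 counts its 70 days from the end-of-study visit.

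**Definition of a TEAE.** SAP 3.6.2: "Treatment-emergent adverse events (TEAEs) are defined as AEs that occur or worsen on or after the first dose of study drug". This follows protocol 9.2.1.5: "TEAEs are defined as any AE occurring or worsening on or after the first dose of study drug". The date algorithm in SAP Appendix A compares dates only with the start of study drug, for example "If start date < study drug start date, then not TEAE". It has no upper limit.

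**Planned summaries.** Protocol 10.6.3, repeated in the synopsis, asks for one AE summary of everything reported. It also asks for a breakdown that is bounded in time: "by study part as well as study period, i.e., up to and including 70 days post last dose of study treatment". SAP 3.6.2 lists an AE overview, tables by system organ class and preferred term, tables by highest grade, and patient listings. None is restricted to 70 days; in that section the 70 days appear only as a collection window. SAP section 6, which records changes from the protocol's analysis, does not mention the missing summary.

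**The concern.** Incidence and severity of TEAEs, with a focus on irAEs, is a primary endpoint in Parts A, A-2 and B (SAP 2.6.1, 2.7.1, 2.8.1). SAP 3.1.5 plans no hypothesis testing, so the descriptive AE tables are the safety result.

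Within 70 days of last dose every AE is reportable. Beyond it only treatment-related SAEs, late irAEs and (under protocol 9.2.5 and 9.2.6) fatal SAEs are. With no end date on TEAEs, events from both periods enter the same TEAE, treatment-emergent SAE, drug-related and irAE tables. A late event can therefore raise only rows that contain those selected kinds, while a late event of any other kind is never counted. A table limited to the fully collected period would show incidence under a single rule. The protocol asked for such a table and the SAP has none.

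**Working it through.** There is no power, alpha or sample-size figure to reproduce. The check is a comparison of texts, followed by a scale calculation.

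**Step 1. Does an event after day 70 count as a TEAE?** Take an irAE with onset 80 days after last dose. It is reportable (SAP 3.6.2, protocol 9.2.2). Its start is after study drug start, so Appendix A classes it as a TEAE. It enters the TEAE and irAE tables. A non-serious, unrelated AE, not immune-related, on the same day is not reportable and cannot enter.

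**Step 2. Can such events arise at a planned contact?** Protocol Table 7-1 puts Follow-up Visit 3 at 90 ± 7 days after discontinuation, that is days 83 to 97. If discontinuation is taken as the last-dose date (an assumption), this is 83 − 70 = 13 to 97 − 70 = 27 days after full collection ends. Survival telephone contacts then follow every 3 months.

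**Step 3. Which planned outputs separate the two periods?**

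| Summary | Protocol 10.6.3 | SAP 3.6.2 |
|---|---|---|
| All reported AEs | yes | yes |
| Up to 70 days after last dose | yes | none |
| Omission declared in SAP section 6 | – | no |

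Section 6 says only that limited enrolment restricts which outputs are produced and that no interim analyses were done. It names no dropped AE summary. Small numbers do not explain the omission either, since a date-restricted version of a planned table needs no more patients than the table itself.

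**Step 4. How far could one late event move a row?** For a patient with no earlier event in that row, the shift is 1/n.

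- A-2, B1, B7 (5 patients each, SAP section 6): 1/5 = 20 percentage points.
- B8 (10 patients, SAP section 6): 1/10 = 10 points.
- All parts: 26 exposed in Part A (protocol 5.3.2) + 5 in A-2 + 20 in Part B (5 + 5 + 10) = 51, assuming all enrolled were dosed; 1/51 ≈ 2 points.

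If the patient already has an event in that row, the shift is zero. The documents give no count of late events, so these are shifts per event, not expected effects.

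**Step 5. Are the late-collection rules consistent?** No.

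| Source | 70 days counted from | Still reportable afterwards |
|---|---|---|
| SAP 3.6.2 | last dose | related SAEs, late irAEs |
| Protocol 9.2.2 | last dose | related SAEs, late irAEs |
| Protocol 9.2.5 | last dose | the same, plus fatal SAEs |
| Protocol 9.2.6 (SAEs) | end-of-study visit | fatal SAEs, related SAEs, late irAEs |

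Collection becomes selective under each rule, but the boundary and content differ. SAP 3.6.2 also cites protocol 9.2.4 for the collection period, whereas the rule stands in 9.2.2.

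**The case against.** The strongest reply is that the SAP follows the protocol. The open-ended TEAE definition is the protocol's, and so is the all-reported-data summary, so mixed tables are themselves specified. Protocol 10.1 allows the SAP to modify the statistical methods. The trial closed early, nothing is tested, and all AE data are listed by patient, so a reader could rebuild a 70-day count by hand. Much of this stands. What remains is that the companion summary is missing and section 6 does not say so. Listings do not replace a summary that the protocol names.

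A reader might infer more than the documents support:

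- *That the SAP mis-defined TEAEs.* It did not; it adopted protocol 9.2.1.5.
- *That no unrelated event can enter after day 70.* Protocol 9.2.5 and 9.2.6 keep fatal SAEs.
- *That irAE rates must rise with length of survival follow-up.* This would need active late ascertainment. After Visit 3 the scheduled contact is a telephone call about survival, and under protocol 9.2.2 later SAE notification depends on the investigator learning of the event.
- *That groups are shown to be non-comparable because Part A patients had 1 to 19 infusions.* That range describes time on treatment, not follow-up beyond 70 days after last dose. The documents show no difference between groups in the latter.
- *That the TEAE definition should be cut off at day 70.* This would contradict protocol 9.2.1.5, remove the all-reported-data summary, and take late irAEs out of the irAE tables.

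**Conclusion.** The point holds as an undeclared omission. The protocol asks for two AE summaries and the SAP supplies one, leaving a primary safety endpoint without incidence tables confined to the period of uniform collection. Any late event can add only to rows containing related SAEs, irAEs or fatal SAEs.

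The realised effect is unknown and may be small or nil. The per-event shifts of 20, 10 and about 2 points are simply 1/n. They rest on the enrolment figures in SAP section 6, on the patient having no earlier event in that row and, for the last, on all enrolled patients having been dosed. In a descriptive study that closed early this is a modest reporting gap, worth repairing because the repair is cheap.

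**What to change.** 1. Keep the TEAE definition and the all-reported-data tables unchanged.
2. In SAP 3.6.2 and Appendix A add a flag for AEs with onset or worsening from first dose through 70 days after last dose, with a rule for partial dates at the upper limit.
3. Produce the TEAE, treatment-emergent SAE, drug-related and irAE incidence tables for flagged events as well, and identify later events separately.
4. If the 70-day summary is left out on purpose, say so in SAP section 6 and give the reason.
5. Reconcile protocol 9.2.2, 9.2.5 and 9.2.6 with SAP 3.6.2 on fatal SAEs and on the date from which the 70 days run, and correct the SAP's cross-reference to protocol 9.2.4.

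The cost is one date condition in the derivation, some wording, and one extra set of tables. No new data are needed.

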9.2.1.2 Events Meeting the AE Definition

- Any abnormal laboratory test results (hematology, clinical chemistry, or urinalysis) or other safety assessments (e.g., ECG, radiological scans, vital signs measurements), including those that worsen from baseline, considered clinically significant in the medical and scientific judgement of the Investigator (i.e., not related to progression of underlying disease).
- Exacerbation of a chronic or intermittent pre-existing condition including either an increase in frequency and/or intensity of the condition.
- New conditions detected or diagnosed after study drug administration even though it may have been present before the start of the study.
- Signs, symptoms, or the clinical sequelae of a suspected drug-drug interaction.

- Signs, symptoms, or the clinical sequelae of a suspected overdose of either study drug or a concomitant medication. Overdose per se will not be reported as an AE/SAE unless it is an intentional overdose taken with possible suicidal/self-harming intent. Such overdoses should be reported regardless of sequelae.
- "Lack of efficacy" or "failure of expected pharmacological action" per se will not be reported as an AE or SAE. Such instances will be captured in the efficacy assessments. However, the signs, symptoms, and/or clinical sequelae resulting from lack of efficacy will be reported as AE or SAE if they fulfill the definition of an AE or SAE.

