10.6.6 Adverse Events

Adverse events will be coded using the most current version of the MedDRA. Incidence tables will be presented for all AEs by maximum grade according to CTCAE v5.0. Adverse events, SAEs, TEAEs, TRAEs (i.e., assessed as at least possibly related to study drug by the Investigator), and AEs resulting in dose reduction, interruption, or discontinuation of study drug will be tabulated, as well as AEs leading to additional therapy. Dose-limiting toxicity will also be tabulated. Summaries for deaths on study will be provided by system organ class and preferred term. Adverse event of special interest for NM21-1480 will be identified according to the most recent case retrieval strategy prior to database lock. Such categories consist of 1 or more well defined safety events which are similar in nature and for which there is a specific clinical interest in connection with the study treatment. For each specific category, number and percentage of patients with at least 1 event will be reported. Additional analyses (including time to onset and duration) may also be performed for these events.

Adverse event of special interest do not require expedited reporting to the Sponsor unless the event(s) meets SAE reporting criteria ([Section 9.2.6](#)).

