3.6.3 Clinical Laboratory Tests

The number and percentage of patients with the following abnormalities will be presented:

- ALT $\geq 3 \times \text{ULN}$, $\geq 5 \times \text{ULN}$, $\geq 10 \times \text{ULN}$, and $\geq 20 \times \text{ULN}$
- AST $\geq 3 \times \text{ULN}$, $\geq 5 \times \text{ULN}$, $\geq 10 \times \text{ULN}$, and $\geq 20 \times \text{ULN}$
- Total bilirubin $\geq 2 \times \text{ULN}$
- Potential Hy's Law cases: ALT or AST $> 3 \times \text{ULN}$, total bilirubin $\geq 2 \times \text{ULN}$, and ALP $< 2 \times \text{ULN}$ at the same visit

Selected clinical laboratory evaluations (i.e., chemistry and hematology) may be summarized using descriptive statistics or CTCAE grade shift tables as appropriate.

All local laboratory assessments, including chemistry, coagulation, hematology, thyroid function will be listed by patient. Applicable chemistry (Alanine Aminotransferase, Albumin, Alkaline Phosphatase, Amylase, Aspartate Aminotransferase, Bilirubin, Creatinine, Glucose, Lactate Dehydrogenase, Lipase, Potassium, Sodium), and hematology (Eosinophils, Hemoglobin, Leukocytes, Lymphocytes, Neutrophils, Platelets) parameters will be graded according CTCAE v5.0. For some laboratory tests, the CTCAE criteria may include qualifying definitions (e.g., clinical AE and/or requirement for concomitant medication) in addition to the specific laboratory value used for the definition of the toxicity grades. For such tests, the qualifying definitions will not be used for the assignment of toxicity grades.

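### SAP 3.6.2 drops the protocol's case-retrieval method and per-category AESI counts without declaring it, leaving ALT/AST above 3-fold baseline with no planned count

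*SAP*

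**What the plan says.** Protocol 10.6.6 sets both the method and the output. On method: "Adverse event of special interest for NM21-1480 will be identified according to the most recent case retrieval strategy prior to database lock". On output: "For each specific category, number and percentage of patients with at least 1 event will be reported".

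SAP 3.6.2 lists six AESI items, taken from protocol 9.2.1.6, and then gives a different method: "AESI's will be identified by the investigator and recorded in the eCRF". Two summaries follow. The first is a single line in the overview table, beginning "Any TEAEs of special interest (overall, by maximum severity, and grade" and running on to Grade 3 or higher. The second comes from the group of tables where patients with events "will be summarized by system organ class (SOC) and preferred term (PT) for the following types of AEs", a group that includes special-interest events. No count per AESI category is planned. A separate AESI listing is.

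SAP 3.6.3 adds a liver table that does not depend on AESI identification: "The number and percentage of patients with the following abnormalities will be presented". Its rows are ALT and AST at or above 3, 5, 10 and 20 times ULN, bilirubin at or above 2 times ULN, and potential Hy's Law cases.

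SAP Section 6, which records changes from the protocol analysis, mentions low enrolment and the cancelled interim analyses. It says nothing about AESIs.

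**The concern.** Two things change between the documents. Identification moves from a retrieval strategy fixed before database lock to the investigator's own identification, and the per-category patient counts disappear. Neither change is declared. Low enrolment explains dropping an interim analysis, but it does not explain dropping a simple count.

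The liver is where this matters. Protocol 5.1 describes dose-dependent hepatitis with an earlier agonistic 4-1BB antibody, and protocol 5.3.2 supports the benefit-risk case partly by noting a single treatment-related Grade 3 transaminase elevation in Part A. ALT or AST more than 3-fold above baseline is the AESI item that can pick up smaller liver signals, since it carries no grade threshold. If that item is not counted, the final report lacks a liver safety figure that the protocol defines.

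**Working it through.** The plan states no figure for this point, so there is none to reproduce. The check has three steps.

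**Step 1. Which AESI items can be counted elsewhere?** Inputs: the item list in protocol 9.2.1.6 and SAP 3.6.2; the planned tables in SAP 3.6.1 to 3.6.3.

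| AESI item | Other planned count, independent of the AESI record |
|---|---|
| Any AE of Grade 3 or higher | Yes: Grade ≥3 overview line and table |
| Hepatobiliary class, Grade ≥3 | Yes: class row of the Grade ≥3 table |
| Immune system class, Grade ≥3 | Yes: class row of the Grade ≥3 table |
| Infusion reaction, Grade 3 or 4 | Yes: preferred-term rows of the Grade ≥3 table |
| DLT or delayed DLT | DLTs: yes, SAP 3.6.1. Delayed DLTs: no separate count |
| ALT/AST more than 3-fold above baseline | No |

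The first item contains the next three. Only the last two can add events below Grade 3. The AESI table is therefore the Grade ≥3 table plus those two items. That overlap comes from the protocol's definition, which the SAP repeats. Within the AESI table, a preferred term carries no ratio to baseline, so the ALT/AST item cannot be read from it.

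**Step 2. Does SAP 3.6.3 cover the ALT/AST item?** Let the baseline be b × ULN. The item is met above 3b × ULN; the lowest row is reached at 3 × ULN. If b < 1, values above 3b and below 3 × ULN meet the item but reach no row. If b ≥ 1, every patient who meets the item is in the ≥3 × ULN row, because 3b ≥ 3. Inclusion criterion 15 allows b up to 2. The values of b below are assumed, to show the range.

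| b | Item met above (× ULN) | Band reaching no row (× ULN) |
|---|---|---|
| 0.3 | 3 × 0.3 = 0.9 | 0.9 to 3 |
| 0.5 | 3 × 0.5 = 1.5 | 1.5 to 3 |
| 0.8 | 3 × 0.8 = 2.4 | 2.4 to 3 |
| 1.0 | 3 × 1.0 = 3.0 | none |
| 2.0 | 3 × 2.0 = 6.0 | none |

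The rows also err the other way. At b = 2 a patient enters the ≥3 × ULN row at 3/2 = 1.5 times baseline, without meeting the item. The ULN rows therefore do not substitute for a baseline-ratio count.

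**Step 3. What does one missed patient weigh?** Inputs: SAP Section 6 gives 5 patients in B1, 5 in B7, 10 in B8 and 5 in Part A-2. Protocol 5.3.2 gives 26 exposed in Part A.

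- B1, B7 or Part A-2: 1/5 = 20 percentage points
- B8: 1/10 = 10 points
- Part B: 5 + 5 + 10 = 20, so 1/20 = 5 points
- All parts: 26 + 5 + 20 = 51, so 1/51 = about 2 points

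The documents give no AESI counts and no rate of missed identification, so an actual under-count cannot be computed.

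**The case against.** A reader might infer that hepatic AESIs are under-counted and hidden. The documents do not support that.

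- A Grade 3 or higher hepatobiliary, immune or infusion-reaction event that is not identified as an AESI is still counted in the Grade ≥3 table. The AESI table is itself split by class and term, AESIs are listed by patient, and all local laboratory values are listed.
- It is tempting to argue that an ALT/AST rise escapes because protocol 9.2.1.2 makes a laboratory abnormality an AE only if "considered clinically significant in the medical and scientific judgement of the Investigator". But protocol 7.2.5.1 and 9.2.1.6 require rises of more than 3-fold above baseline to be reported as AESIs, with no such condition. Sites following the protocol should report them. (Protocol 10.6.6 says AESIs need expedited reporting only when SAE criteria are met, whereas 9.2.1.6 treats all of them like SAEs. The two sections must be reconciled.)
- Protocol 10.1 lets the SAP modify methods. The retrieval strategy is not among the documents, and 10.6.6 does not say that its categories are the six items of 9.2.1.6.
- Some uncounted rises would be clinically small. At b = 0.3 the threshold of 0.9 × ULN is still below ULN.

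All of this stands, and it narrows the point. What it leaves is one protocol-defined liver item with no planned count other than through investigator identification. The SAP has no derivation to fall back on and no reconciliation. SAP 3.1.7 has a conservative rule for missing causality but none for an AESI that was not identified. The grade shift tables in SAP 3.6.3 are optional, and the SAP defines no 3-fold-baseline category for them. Freedom to change a method also does not remove the reason to record the change in the section kept for that purpose.

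**Conclusion.** The concern holds in a limited form. SAP 3.6.2 departs from protocol 10.6.6 on both identification and per-category counts, and Section 6 does not say so. The practical loss is mainly one item, ALT/AST more than 3-fold above baseline, in patients whose baseline is below ULN and whose values lie between 3 times baseline and 3 times ULN. Delayed DLTs also lack a count of their own. Under-counting is a risk that depends on identification by investigators and is not demonstrated. One missed patient would shift a rate by between about 2 points (all 51 patients) and 20 points (a group of 5). Reading the protocol's categories as the six listed items is an assumption. The gap in the ALT/AST rows does not depend on it: it follows from the two thresholds alone and needs no assumed ULN in U/L. The change is worth making, but the documents give no ground for saying that a liver signal has been concealed.

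**What to change.** 1. In SAP 3.6.3, add rows for patients, n (%), with any post-baseline ALT more than 3 times baseline, and the same for AST. Derive them from local laboratory values and show them by dose level and cohort.
2. In SAP 3.6.2, derive the objective AESI items by program from grade, system organ class, infusion-reaction data and laboratory values. Keep DLTs and delayed DLTs as the investigator records them. Report n (%) of patients for each category and reconcile the result with the AESI record in the eCRF, showing disagreements in the AESI listing.
3. In SAP Section 6, record whatever departure from protocol 10.6.6 remains, with the reason.

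The cost is a few lines of SAP text and one small extra table from data already collected. The AESI count may rise slightly, and some of the added cases will be clinically minor.
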